## Prohibited & concomitant meds

Prohibited medication/class of drug:	Usage:
Any investigational anticancer therapy other than those under investigation in this study	Should not be given concomitantly whilst the patient is on study treatment
mAbs against CTLA-4, PD-1, or PD-L1 other than those under investigation in this study	Should not be given concomitantly whilst the patient is on study treatment
Any concurrent chemotherapy, radiotherapy, immunotherapy, or biologic or hormonal therapy for cancer treatment other than those under investigation in this study	Should not be given concomitantly whilst the patient is on study treatment. (Concurrent use of hormones for non-cancer-related conditions [e.g., insulin for diabetes and hormone replacement therapy] is acceptable. Local treatment of isolated lesions, excluding target lesions, for palliative intent is acceptable [e.g., by local surgery or radiotherapy])
Live attenuated vaccines	Should not be given through 30 days after the last dose of IP

## 5 CORRELATIVE STUDIES FOR RESEARCH

### 5.1 BIOSPECIMEN COLLECTION

Please note that tubes and media may be substituted based on availability with the permission of the PI or laboratory investigator.

#### 5.1.1 Blood studies

##### 5.1.1.1 Serum circulating/Blood cytokine profile

Refer to the table in section [5.2](#) for volume, tube types and sample collection schedule. Samples will be assessed for:

- IL-1B, IL-2, IL-4, IL-6, IL-8, IL-10, IL-12p70, IL-13, IL-18, IFN- $\gamma$ , IL-6, TNF-alpha, and IL-10. This will be done with a commercial ELISA kit such as V-plex in collaboration with [name], and [name].
- Soluble PD-L1 (total and free unbound PD-L1)

For Serum collection of samples for cytokines and soluble PDL-1, please e-mail [[contact]](mailto:[contact]) at least 24 hours before transporting samples (the Friday before is preferred). For sample pickup, page [name]. For immediate help, call [contact] (main biospecimen processing core number) or, if no answer, [contact] (main clinical pharmacology lab number). For questions regarding sample processing, contact [[contact]](mailto:[contact]).

##### 5.1.1.2 PBMCs for immune analysis

Samples will be collected at the timeframes indicated in the table in section [5.2](#)

- Flow cytometry of immune subsets (include CD4+ and CD8+ T-cells, Tregs, NK

cells, and MDSCs and PD-L1 expression on immune cells) – This will be processed in [name] laboratory as described below. [name] laboratory now has the ability to analyze 123 peripheral immune cell subsets as shown in [Appendix D](#).

- T-cell clonal expansion assay if appropriate funding and material is available
- Antigen-specific responses of cytotoxic lymphocytes for tumor associated antigens (e.g. brachyury, EPCAM)
- Immunogenicity Assessment (anti-durvalumab antibodies and anti-vicineum antibodies) – Samples will be collected at baseline and stored in [name]
  - i. Week 8 for ADA and Week 12 for AVA (separate blood collection at the weeks specified – Stored in [name]

#### **5.1.1.2.1 Sample processing**

For PBMCs, green top tubes will be obtained and then processed at the Clinical Services Program (CSP) NCI Frederick Cancer Research and Development Center, [name] in collaboration with [name] research group. On days samples are drawn, [name] at CSP should be notified (phone: [name]; fax [name]). Once a patient's treatment schedule has been determined, [name] should be notified at [contact] for planning purposes. [name] and colleagues recently published their ability to analyze PBMCs for 123 subsets of peripheral immune cells using 30 unique markers in 5 immune flow cytometry panels. These subsets are subsets of CD4+ T cells, CD8+ T cells, Tregs, B cells, NK cells, NK-T cells, conventional dendritic cells (cDCs), plasmacytoid DCs (pDCs), and MDSCs. A full list is enclosed in [Appendix D](#).

### **5.1.2 Research urine studies**

#### **5.1.2.1 Urine cytokines**

Urine collection at the timepoints indicated in the table in section [5.2](#) for correlative/exploratory research aims (e.g. inflammatory cells, cytokines) at baseline. This will be performed through a commercial vendor, Luminex, using a platform of 12 urinary cytokines.

#### **5.1.2.2 Urine EpCAM, Pharmacokinetics and Pharmacodynamics**

This will be done in direct collaboration with [name] laboratory

- Evaluate PK for urinary Vicineum by testing for VB4-845 – see table in section [5.2](#) for PK timepoints
- Evaluate pharmacodynamics (PD) for EpCAM shedding in the urine [baseline, first void after drug administration in Week 1, first void the next morning after treatment, and the day 8 void prior to start of week 2 treatment, Week 6 before Vicineum, Week 10 before Vicineum, Week 12 before Vicineum - – see table in section [5.2](#) for PD timepoints
- Evaluate EpCAM in the urine for the ability to monitor or predict response to therapy - see table in section [5.2](#) for PK timepoints

### 5.1.2.3 Sample Processing

For urine collection, it will be processed according to standard protocol (refer to [Appendix E](#)) and stored in the Urologic Oncology Branch in [name] lab. Samples will be batched at the end of the trial and then analyzed.

### 5.1.3 Tissue studies

Samples will be obtained pre-and post treatment as indicated in the table in section [5.2](#) to:

- Perform immunohistochemistry (IHC) or cytogenetic analysis of baseline tissue (FFPE or frozen tissue specimen) for EpCAM, PD-1/PD-L1, TILS, CD4, CD8, Tregs, MDSCs, Macrophages, and monocytes. In addition, mesenchymal markers such as vimentin, TWIST, Snail, Slug, and Sip1 may also be assessed by immunohistochemistry of baseline tissue. This can be compared to similar IHC of tissue obtained from the last biopsy on trial. This analysis will be performed by the NCI Laboratory of Pathology upon accruing at least 4 patients or by PI's discretion. Baseline FFPE slides will be obtained from paraffin-embedded blocks stored within NCI's Laboratory of Pathology at a future date when analysis will be performed. In the event that patients have had baseline biopsy at an outside institution, every effort will be made to obtain the paraffin-embedded blocks in order to generate baseline FFPE slides for further analysis.

In particular to the current study, we would like to study the T-cell infiltration pattern within bladder tumors pre- and post-treatment. Specifically, we will look at:

1. The presence of CD4 and CD8 T cells in bladder tumor specimens pre- and post-treatment
2. The presence of regulatory T cells (Tregs) by double staining with FoxP3 and CD4 in bladder tumor specimens pre- and post-treatment
3. The presence of myeloid derived suppressor cells (MDSC) in bladder tumor specimens pre- and post-treatment
4. The presence of myeloid derived suppressor cells (MDSC) in bladder tumor specimens pre- and post-treatment
5. The presence of PD-L1 staining pre- and post-treatment as specified below in section [5.1.3.2](#).
6. The presence of EpCAM and mesenchymal markers.

- If sufficient tissue is available, cell lines may be generated. Cell lines may be characterized by karyotyping, interphase fluorescence in situ hybridization (FISH) mapping, immunohistochemistry, and/or flow cytometry. Differences between cell lines will be manipulated to study the various molecular pathways active in nutrient sensing, cell cycle, cell signaling, proliferation, apoptosis, angiogenesis, and metastatic potential in urothelial cancer.
- If adequate tissue and funding available, then may perform mutational load analysis through a targeted panel (RNAseq or DNA mutation panel) of tumor tissue. This analysis will be performed by the NCI CORE facility, NCI collaborator ([name]), or outside entity (e.g. Foundation Medicine)

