### **3.2.2 Vicineum™**

#### **3.2.2.1 Doses And Treatment Regimens**

The initial dose of vicineum is 30 mg in 50 mL of saline (Dose level 1). Vicineum will be instilled through a catheter into the bladder. Subjects will be instructed to hold study drug in the bladder for 2 hours, and asked to refrain from fluid intake to reduce urine flow during this period. After complete administration of the Vicineum dose, the catheter may be clamped and remain in for the 2-hour dwell time, or may be removed, per the discretion of the investigator.

Subjects will be encouraged, when physically possible, to be upright (sitting or standing), prone, supine, and in the left and right lateral decubitus positions, for at least 15 minutes each, in any order. If physically unable, this should be recorded in the CRF. At the end of 2-hour period, the catheter will be unclamped and the bladder will be drained (if the catheter remained in place) or the subject will void to empty the bladder.

Study Phase	Treatment Regimen
Induction Phase (Weeks 1-12)	One intravesical dose of Vicineum in 50 mL of saline instilled once weekly for a total of 12 weeks.
Maintenance Phase (up to Week 104)	One intravesical dose of Vicineum 50 mL saline instilled once every other week for 12 months from the start of the Induction phase. Please note, at the end of each maintenance cycle there is a 2 week window in order to allow the patients sufficient time to recover from biopsies prior to continuing treatment. Refer to the schema for a detailed description of Vicineum administration weeks. If remain disease-free, therapy can be continued for up to 24 months (Week 104) from the start of the Induction Phase.

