- Sponsor or Manufacturer terminates the study
- The FDA requests that the sponsor terminate treatment of a specific subject or subjects or all subjects
- Subject noncompliance that, in the opinion of the investigator or sponsor, warrants withdrawal; e.g. refusal to adhere to scheduled visits
- Investigator discretion
- Positive pregnancy test or intent to become pregnant or intent to breast-feed or is breastfeeding
- Disease recurrence with high-grade bladder cancer

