#### 5.1.3.2.1 Sample collection for PD-L1 testing

- The preferred tumor sample for the determination of a patient's PD-L1 status is the one taken following the completion of the most recent prior line of therapy. Samples taken at this time reflect the current PD-L1 status of the tumor and considered clinically most relevant.
- In AstraZeneca studies, the preferred sample for PD-L1 testing was less than or equal to 3 months old. In cases where a sample a less than 3 months old was not available, patients

were asked to undergo a new biopsy if considered clinically appropriate by their treating physician.

- Samples should be collected via a core needle of 18 gauge or larger or be collected by an incisional or excisional tumor biopsy. Where institutional practice uses a smaller gauge needle, samples should be evaluated for tumor cell quantity (i.e. >100 tumor cells) to allow for adequate PD-L1 immunohistochemistry analyses.
- When the collection of a new sample is not clinically appropriate, archival samples may be utilized provided the specimen is not older than 3 years of age. When archival samples are used to assess PD-L1 status, the age of the sample / date of collection should be captured.
- Samples submitted for PD-L1 testing should be formalin fixed and embedded in paraffin. Samples from fine needle aspirates (FNA) or decalcified bone are not appropriate for PD-L1 analysis.

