## 5.2 SAMPLE COLLECTION SCHEDULE

Test/assay	Volume blood (approx)	Type of tube a	Collection point (+/- 7 days)	Location of specimen analysis
Urine collection for Urinary Cytokines (Section 5.1.2)	50-100 mLs	Urine specimen cup	Baseline, 3 months, 6 months	Stored and processed in [name] Lab ( Appendix E ) using Luminex Assay
Serum collection for cytokines (section 5.1.1)	20 mLs	2 Red Top (SST) Tubes	Baseline, 2 weeks, 3 weeks, 5 weeks	Stored in [name]
Plasma collection for soluble PD-L1 (secion 5.1.1)	6 mLs	EDTA	Baseline, 2 weeks, 3 weeks, 5 weeks	Stored in [name]
Urinary PK for Vicineum (Section 5.1.2.2)	50-100 mLs	Urine specimen cup	Baseline, First void after Week 1 Vicineum, First void morning after Week 1 Vicineum, Day 8 void prior to Week 2 Vicineum	Stored in [name] Lab ( Appendix E )
Urinary EpCAM (Section 5.1.2.2)	50-100 mLs	Urine specimen cup	Baseline, First void after Week 1 Vicineum, First void morning after Week 1 Vicineum, Day 8 void prior to Week 2 Vicineum, Week 6 before Vicineum, Week 10 before Vicineum,	Stored in [name] Lab ( Appendix E )

Test/assay	Volume blood (approx)	Type of tube a	Collection point (+/- 7 days)	Location of specimen analysis
			Week 12 before Vicineum	
Gene Expression (see section 5.4.1 )	Single FFPE slide or frozen tissue	N/A	Baseline	Stored in [name] Lab and processed by NCI DTB CTU lab or NCI CORE
Tissue IHC (see section 5.1.2 )	Single FFPE slide	N/A	Baseline, Last Biopsy on Trial	Will be obtained from tissue blocks in Laboratory of Pathology and analyzed by [name] (Laboratory of Pathology)
RNAseq and/or DNA mutational panel for mutational load (see section 5.1.2 )	Single FFPE slide or frozen tissue	N/A	Baseline	NCI CORE facility or outside entity (Foundation Medicine)
PBMCs for immune subsets, antigen specific responses (section 5.1.1.2 )	60 mL	6 green top Tubes	Baseline, 3 months, 6 months	[name] Laboratory (Deliver to Frederick Lab)
Immunogenic Assessment (ADA, AVA) (section 5.1.1.2 )	8 mL	2 lithium heparin (4 mL each) tubes	Baseline, Week 8 (ADA), Week 12 (AVA)	[name] Laboratory in collaboration with AZ and Sesen Biotherapeutics

a. Please note that tubes and media may be substituted based on availability with the permission of the PI or laboratory investigator.

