#### **6.2.3 Response Criteria**

Patients will be evaluated every 3 months as per standard of care with cystoscopy. Biopsy will be done at PI discretion pending cystoscopic findings. Any biopsies done will be for clinical reasons to rule out tumor recurrence, however, extra biopsy material if available will be used for research purposes.

Evaluable for toxicity: All patients will be evaluable for toxicity from the time of their first treatment with vicineum or durvalumab. All observed toxicities will be tabulated using CTCAE v5.0.

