## **10.2 SAMPLE SIZE DETERMINATION**

The trial will begin with a 3-patient run-in at the proposed doses of Vicineum and durvalumab (1500mg; 30 mg) and if 0/3 or 1/3 patients have a DLT, then the next 3 patients will also be treated at the full doses of the agents (1500mg durvalumab; 30 mg Vicineum). If 0/6 or 1/6 has a DLT, then the remaining 18 patients will be treated at the full doses if the cumulative fraction of patients experiencing a DLT is <1/3.

If 2 or more patients among 3 to 6 have a DLT at 1500mg durvalumab and 30mg Vicineum, then 3 patients will be enrolled at the lower dose level (1500mg durvalumab and 20mg Vicineum), and if 0/3 or 1/3 patients have a DLT, then the next 3 patients will also be treated at the reduced doses of the agents. If 1/6 has a DLT, then the remaining patients will be treated at the lower dose level of the agents (1500mg durvalumab and 20mg Vicineum) if the cumulative fraction of patients experiencing a DLT is <1/3.

As the secondary endpoint, all the evaluable patients will have determinations of many immune parameters at baseline, 3 months, and 6 months. The changes in the parameters obtained from blood samples will be determined at baseline vs. 3 months, and baseline vs. 6 months. The changes in the parameters obtained from biopsies will be obtained from baseline vs. a single second biopsy at 6 months. A very large number of parameters may be evaluated, and unless more parameters than anticipated are to be evaluated, we will assume that 24 patients will be adequate to evaluate changes in these parameters based on the following. As an illustration, we will assume that a total of 25 paired tests will be considered of equal, primary importance. Paired results from 24 evaluable patients, including those used in the initial run-in portion who are treated at the highest safe dose, will provide 90% power to detect a change from baseline of 1.0 SD of the change (effect size=1.0) using a two-sided 0.002 significance level paired t-test, to allow an overall 0.05 significance level test, applying a very conservative Bonferroni adjustment to the set of approximately 25 paired comparisons. In practice, comparisons of the paired values will likely be performed using a Wilcoxon signed rank test instead of a paired t-test, and a Hochberg adjustment may be used instead of an overly stringent Bonferroni adjustment.

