Urinary EpCAM will be measured and will be compared between patients who have a clinical response to therapy vs. those who do not respond. The results will be presented for both response categories using descriptive statistics such as mean, standard error, median, minimum, maximum and other descriptive measures. Although it is expected to have low power, a comparison of the EpCAM levels may be compared between the two response categories using a Wilcoxon rank sum test, with the resulting p-value intended to help describe the differences noted.

PD-L1 and PD-1 levels will be obtained at baseline and after treatment with both agents. The change in levels will be determined between the two measurements, and these changes will be compared between responders and non-responders, as well as between those who respond or have SD (clinical benefit=CR+PR+SD) and those with PD. Although it is expected to have low power, in each case the comparisons between the two response categories will be made using a Wilcoxon rank sum test, with the resulting p-value intended to help describe the differences noted.

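### The post-treatment tissue sample is defined in two incompatible ways; under the collection schedule its timing depends on outcome, so the PD-L1/PD-1 comparison by response is confounded with time on drug

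*Combined protocol and SAP*

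**What the plan says.** **Collection.** Section 5.1.3 says of the baseline immunohistochemistry: "This can be compared to similar IHC of tissue obtained from the last biopsy on trial". The tissue row of the table in 5.2 reads "Baseline, Last Biopsy on Trial". The calendar in 3.4 gives the same timing for the EpCAM determination, the tissue PD-L1 assay and the tissue immune correlates.

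**Analysis.** Section 10.2 states: "The changes in the parameters obtained from biopsies will be obtained from baseline vs. a single second biopsy at 6 months". Section 10.4.3 repeats this for the paired tests. For PD-L1 and PD-1, 10.4.3 measures the change between baseline and a point after both agents have been given, names no week, and adds that "these changes will be compared between responders and non-responders", using a Wilcoxon rank sum test.

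**What decides when the last biopsy falls.** Section 3.6.1 lists "Disease recurrence with high-grade bladder cancer" among the events that end protocol treatment. Section 3.2.2.1 lets disease-free patients continue to week 104. Evaluations are 3-monthly, but under 6.2.3 "Biopsy will be done at PI discretion pending cystoscopic findings".

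**Baseline tissue.** For PD-L1, 5.1.3.2.1 prefers tissue taken after the most recent prior therapy. Where a new sample is not clinically appropriate, "archival samples may be utilized provided the specimen is not older than 3 years of age", with sample age recorded. In 2.1.1.1 the 12-week biopsy window stands in the Ta/T1 bullet; the CIS bullet states none. Section 2.1.1.3 puts the last BCG dose within a year of enrollment for subjects who qualify under 2.1.1.2.

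**The concern.** PD-L1 and PD-1-expressing T cells in paired biopsies, as a marker of response or benefit, are a named secondary objective (1.1.2, 10.1). If the last biopsy is used, non-responders are sampled early and durable responders late. Any marker that drifts with time on treatment would then differ between the groups even if it had nothing to do with response. The pooled paired change in the other tissue markers would average over exposures of very different length. If the 6-month rule is used instead, the timing is common but patients who recur earlier have no sample, and the 24 pairs behind the stated power are not available. The documents do not say which rule governs.

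At the other end of the pair, PD-L1 baseline tissue that predates the last BCG course would let a BCG effect be counted as change on the combination.

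**Working it through.** **1. The two definitions side by side.**

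| Sections | Second tissue sample | Tissue assay scheduled then? |
|---|---|---|
| 3.4, 5.1.3, 5.2 | last biopsy on trial | yes |
| 10.2, 10.4.3 (paired tests) | single biopsy at 6 months | no |
| 10.4.3 (PD-L1/PD-1 by response) | after both agents, no week | not tied to either |

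**2. When the last biopsy falls.** Induction dosing ends at week 12 and dosing resumes at week 15 (3.4), so the first evaluation is taken as about week 13. The schema prints the 24-month evaluation at week 105. By the same pattern the 12-month evaluation is at about week 53, the end of the third maintenance cycle; that position is assumed because the schema symbols are not legible. Failure at the first evaluation gives a last biopsy near week 13. A durable responder's can be as late as week 53 or 105. The spread is realistic: section 1.2.3 reports 5 of 12 patients responding at 12 weeks, about half of them beyond 12 months.

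**3. The plan's own power.** Section 10.2 uses 24 pairs, a change of 1.0 SD and two-sided alpha 0.05/25 = 0.002. For a paired t-test, power = P(T' > t at 1 − α/2), where T' is noncentral t with n − 1 = 23 degrees of freedom and noncentrality 1.0 × √24 = 4.90. This gives 0.902, and 24 is the smallest n that reaches 90%. The stated figure reproduces.

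**4. Power with fewer tissue pairs.** Same formula:

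| Pairs | Basis | Power at 1.0 SD | Change detectable with 90% power |
|---|---|---|---|
| 24 | plan | 0.902 | 1.00 SD |
| 20 | illustrative | 0.793 | – |
| 16 | illustrative | 0.609 | – |
| 12 | 24 × 0.50, historical 6-month DFS in 10.2 | 0.363 | 1.62 SD |
| 10 | 24 × 5/12, interim 12-week response in 1.2.3 | 0.238 | 1.90 SD |

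The last two rows assume that only patients still disease-free (12) or responding at 12 weeks (10) provide 6-month tissue. A recurrence biopsied at the 6-month visit itself would add pairs.

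**5. Size of the timing effect (illustration).** Assumed: 24 × 5/12 = 10 responders and 14 non-responders; non-responders sampled at month 3; five responders at month 6 or 9 and five at month 12; SD of change 1; no true link between marker and response; change drifting linearly with months on drug. Mean responder time is (5 × 7.5 + 5 × 12)/10 = 9.75 months, so the gap is 6.75 months and the spurious difference is about 6.75 × drift. Rank sum test at two-sided 0.05, 5,000 simulated trials per row:

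| Drift (SD/month) | Simulated spurious difference | Rejection, last biopsy | Rejection, all at 6 months |
|---|---|---|---|
| 0 | 0.00 SD | 5.0% | 4.7% |
| 0.05 | 0.35 SD | 12.2% | 5.2% |
| 0.10 | 0.68 SD | 30.9% | 5.2% |
| 0.15 | 1.02 SD | 59.3% | 4.8% |

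The documents give no drift; 0 to 0.15 is an assumed range.

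**6. Baseline PD-L1 tissue.** For subjects under 2.1.1.2, the last BCG dose is at most one year before enrollment. Archival tissue older than about one year at enrollment must therefore predate it: roughly 3 − 1 = 2 of the 3 permitted years. Sample age is captured, but no analysis rule uses it.

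**The case against.** The strongest reply is that section 10 governs the analysis and fixes 6 months, so timing does not depend on outcome; step 5 shows the illustrative rejection rate then stays near 5%. That is right as far as it goes, and it rules out saying that the plan definitely tests the last biopsy. But the collection sections assign no assay to a 6-month biopsy, and the comparison by response never says 6 months.

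Three stronger readings are tempting and are not supported:

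- *Responders and non-responders will differ on CD8, Treg and MDSC change.* Section 10.4.3 plans the response comparison of change only for PD-L1 and PD-1. The other tissue markers come under the pooled paired tests.
- *Cumulative dose at the last biopsy measures the bias.* Dose counts do not measure marker drift. Section 1.2.1.2 reports durvalumab steady state at about week 16. Responders who relapse at 6 or 9 months have earlier last biopsies. With no drift there is no bias.
- *Baseline tissue in general may be three years old.* The allowance is a conditional fallback for PD-L1 only. Recent, post-therapy tissue is preferred, and the calendar places screening biopsies within 12 weeks. The documents do not show that the fallback is used at all.

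It is also fair that an early common timepoint has a selection problem of its own: biopsy is discretionary, so 3-month tissue may come mainly from patients with suspicious cystoscopy. PD-L1 scoring also needs more than 100 tumor cells (5.1.3.2.3), which a complete responder may not provide. Finally, 10.4.3 already calls these comparisons low-powered and their p-values descriptive. Low power does not remove bias, but it limits what rests on the result.

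**Conclusion.** The point holds. The two definitions of the second tissue sample cannot both apply and must be reconciled. If the collection schedule governs, the PD-L1/PD-1 comparison confounds response with time on drug, and the paired change in other tissue markers mixes short and long exposures. The direction and size of any bias are unknown; the illustration runs from none (5% rejection at zero drift) to severe (59% at 0.15 SD per month) and rests on assumed drift, sampling times and group sizes. If the 6-month rule governs, timing is equal but perhaps 10 to 12 of 24 tissue pairs remain, with power 0.24 to 0.36 in place of 0.90.

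The baseline gap is real but narrow: it needs the archival fallback to be used on tissue from before the last BCG dose. The CIS bullet has no biopsy window to prevent that, and no analysis rule excludes or flags such tissue.

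These are secondary analyses with no decision rule attached. The primary safety endpoint is not affected. The change should be made, but the trial's main conclusion does not depend on it.

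**What to change.** - Use one definition of the second tissue sample in 3.4, 5.1.3, 5.2, 10.2 and 10.4.3, set at a common early on-treatment evaluation and drawn from evaluation biopsies already in the calendar. Three months keeps early failures; 6 months loses patients who recur before then.
- Keep the last biopsy as a separate, descriptive sample, and report weeks on drug at every biopsy.
- Report, by response group, how many patients have tissue at the common timepoint and how many samples can be scored, since both may depend on response.
- Restate the tissue power in 10.2 for the expected number of pairs (about 0.61 at 16 and 0.36 at 12).
- Record the date of baseline tissue relative to the last BCG dose. Base the main paired PD-L1 analysis on tissue taken after that dose; use older archival tissue only for baseline description or a sensitivity analysis.

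The cost is wording in these sections, plus biopsy dates and counts in the report; no extra biopsies. The downside is that patients with only late or pre-BCG tissue leave the main paired test, which lowers its power, and discretionary biopsy means that selection at the common timepoint is disclosed but not removed.
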